## 8 ADVERSE EVENTS

### Definitions

#### 8.1 Adverse event (AE)

Any untoward medical occurrence in a patient or clinical investigation subject administered a pharmaceutical product, including laboratory parameters deviations. AE does not necessarily have a causal relationship with the treatment.

#### Causal relationship with investigated treatment

The AE(s) relationship with investigated product(s) will be assessed according to the following categories:

1. The relationship is considered **certain** if an AE developed during the treatment with the product and cannot be explained by concurrent disease or other drugs or chemicals. The response to withdrawal of the drug (dechallenge) should be clinically plausible. The event must be definitive pharmacologically or phenomenologically, using a satisfactory rechallenge procedure if necessary.

2. The relationship is considered **probable** if an AE occurred in a reasonable time sequence to administration of the drug, unlikely to be attributed to concurrent disease or other

drugs or chemicals, and which follows a clinically reasonable response on withdrawal (dechallenge). Rechallenge information is not required to fulfil this definition.

3. The relationship is considered **possible**, if an AE occurred in a reasonable time sequence to administration of the drug, but which could also be explained by concurrent disease or other drugs or chemicals. Information on drug withdrawal may be lacking or unclear.

4. The relationship is considered **unlikely**, if a causal relationship of an AE with the drug cannot be ruled out, but:

- other drugs, chemicals or underlying disease provide plausible explanations,
- temporal relationship of the AE to the drug administration is improbable.

5. AE is considered **unrelated** to the drug administration, if:

- there is a clear alternative explanation of the AE, and/or
- temporal relationship of the drug and the AE is groundless, and/or
- relationship of the drug with the AE is not plausible.

6. The relationship is considered **unassessable**, if the data is insufficient or contradictory and cannot be supplemented or verified.

## **8.2 Adverse reaction (AR)**

Adverse reaction (AR) means a noxious and unintended response to an investigated medical product, **associated** with any dose of the product.

According to the "Detailed guidance on the collection, verification and presentation of adverse reaction reports arising from clinical trials on medicinal products for human use" (April 2006), all adverse events, regarded by an investigator or Sponsor as **having reasonable causal relationship with the medicinal product** are considered AR, that is related to the investigated product.

Based on the above definitions, ARs are all AEs with the following relationship with the investigated product:

- 1 - Certain
- 2 - Probable
- 3 - Possible
- 4 - Unassessable

AE is not considered AR if relationship with the drug is estimated as:

5 - Unknown

6 - Unrelated

### **Seriousness criteria**

AE/AR is considered serious if it:

- Results in death,
- Is a life-threatening event;

**Note:** AE is not considered to be life-threatening if the subject's life was in danger during the AE; this does not apply to events that hypothetically could have led to death if they progressed.

- Requires inpatient hospitalization or prolongation of an existing hospitalization;
- Leads to persistent and significant disability or incapacity;
- Is a congenital anomaly or birth defect;
- Is an important from a medical point of view event that may pose a risk to the patient or may require intervention to prevent one of the outcomes described above. All suspected cases of infectious agents transmission via medicinal product are considered serious and should be evaluated in the category of "medically significant events" if there are no other seriousness criteria.

AE/AR is **not** considered serious if:

- The event does not meet conditions described in the definition of serious AE/AR.

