### **Reporting requirements**

The investigator must report SAEs (both related and unrelated to the investigated product) by faxing the CRF Adverse Event Form pages **no later than 24 hours** after he/she became aware of the SAE:

If safety issues are dealt with directly by Sponsor:

Sponsor medical expert [name],  
[contact], mob. [name]  
[contact]

All serious adverse events must be monitored until the outcome.

Any information and required documents that may be available (copies of results of laboratory tests, procedures, autopsy, cause of death data, etc.) will be provided by the Investigator by means of separate written reports directly to the Sponsor medical expert as soon as possible.

The investigator should comply with applicable local regulations for AR reporting to regulatory authorities/ethics committees.

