### **8.5 Sponsor responsibilities for AE reporting**

The sponsor should ensure that all necessary information about suspected serious and suspected unexpected serious adverse reactions (SUSAR) is duly reported to the regulatory authorities and to Ethics Committees within the appropriate time period after the sponsor became aware of the event (the day when the Sponsor received a SUSAR report):

- fatal and life-threatening unexpected events - not later than 7 days;
- other unexpected serious events - not later than 15 days.

The sponsor should ensure that in case any further information about the event becomes available, all the required data and supporting documents (which may become available in the future) is also duly reported within the time period specified above.

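### The note explaining the life-threatening criterion is inverted; read literally, it moves the sponsor's limit for some non-fatal unexpected reactions from 7 to 15 days

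*Combined protocol and SAP*

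**What the plan says.** The list under Seriousness criteria, in Section 8.2, has six entries: death, life-threatening, hospitalization, disability, congenital anomaly and medically important. The note under the second entry has two halves. The first says that an "AE is not considered to be life-threatening if the subject's life was in danger during the AE". The second adds that "this does not apply to events that hypothetically could have led to death if they progressed".

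The last criterion is broad. It begins "Is an important from a medical point of view event that may pose a risk to the patient" and extends to events needing intervention to prevent one of the outcomes listed before it. An event is not serious if "The event does not meet conditions described in the definition of serious AE/AR".

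Two reporting rules depend on this classification:

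- Section 8.4, Reporting requirements, is triggered by SAE status: "The investigator must report SAEs (both related and unrelated to the investigated product", with a limit of 24 hours.
- Section 8.5 sets the sponsor's limits, counted from the day the sponsor receives the report: "fatal and life-threatening unexpected events - not later than 7 days", and "other unexpected serious events - not later than 15 days".

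**The concern.** The note removes from the life-threatening category the events that the category is meant to hold. It is also the only explanation of the term in the text available to this review.

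The term has a practical function. Section 8.5 uses it to separate the shorter sponsor limit from the longer one. A site or safety reviewer who applies the note as printed would be following the protocol and could still put a dangerous reaction on the slower track. Section 11 has the investigator agree to comply with the protocol's instructions, so correct handling depends on readers setting the printed words aside.

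**Working it through.** No power, alpha or sample-size figure is involved. The check follows one kind of event through Sections 8.2 to 8.5, first as printed and then with *not* removed from the first half of the note.

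**The event.** A non-fatal adverse event, unexpected and judged related (so reportable as a SUSAR under Section 8.3 if serious), during which the patient's life was in danger.

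**Step 1: do the two halves of the note agree?** As printed, the first half excludes actual danger, and the second exempts hypothetical danger from that exclusion. That is the reverse of what a life-threatening criterion needs. With *not* removed, actual danger qualifies and hypothetical danger does not, so both halves agree with each other and with the criterion. This points to a drafting or translation slip.

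**Step 2: which other criteria can keep the event serious?** There are six. Taking away life-threatening (removed by the note) and death (the event is non-fatal) leaves 6 − 1 − 1 = 4: hospitalization, disability, congenital anomaly and medically important. Section 4.2 admits only postmenopausal women, so congenital anomaly is not a realistic route, which leaves 4 − 1 = 3 in practice.

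**Step 3: which reports follow?**

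| Case | Life-threatening | Serious | Investigator report | Sponsor limit |
|---|---|---|---|---|
| *Not* removed | yes | yes | 24 hours | 7 days |
| As printed, at least one other criterion met | no | yes | 24 hours | 15 days |
| As printed, no other criterion judged met | no | no | not triggered | not triggered |
| Fatal event, either wording | not needed | yes, through death | 24 hours | 7 days |

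**Step 4: size.** In the second row the limit moves by 15 − 7 = 8 days. Both limits are upper bounds, so 8 days is the largest difference between the limits and not an expected delay. In the third row, two reports that would have been due are lost: the investigator's 24-hour report and the sponsor's 7-day report. The 7-day and 15-day limits are alternatives for one event, so they do not count as two separate reports.

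**Step 5: does other text repair the note?** Sections 8.3 to 8.5 use the terms serious and life-threatening without redefining them. Section 11 names GCP, and Section 8.4 says "The investigator should comply with applicable local regulations for AR reporting to regulatory authorities/ethics committees". The text of those rules is not in the documents, so they cannot be shown to correct the note.

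**The case against.** The strongest reply is that nobody would be misled. The criterion itself is stated correctly, Section 8.5 uses the ordinary term, and the second half of the note makes sense only if the first half is affirmative. On the main route the sponsor's medical expert still hears of the event within 24 hours. Nor do the documents show that a literal reading would prevail over GCP or local rules. Most of this stands. It makes the slip easy to recognise and limits its likely effect, but the printed definition still says the opposite of its purpose in a rule that sets a reporting limit.

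A reader might go further and infer that dangerous events would commonly go unreported. The documents do not support that. An event in which life was in danger fits the medically important criterion almost by definition, since that criterion covers risk to the patient and intervention to prevent the listed outcomes, of which death is the first. Many such events would also involve hospitalization. The case with no serious-event report therefore exists on paper but is remote. Even there, Section 8.4 requires the event to be recorded as an AE in the CRF.

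**Conclusion.** The note is wrong as written and should be fixed. The realistic consequence is narrow. For a non-fatal, unexpected, related reaction with actual danger to life, the sponsor's limit becomes 15 days instead of 7, while the 24-hour report stands. Loss of both reports due is a remote possibility.

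This rests on two assumptions: that the note is applied literally, and that no outside rule overrides it. The number of such reactions cannot be estimated from the documents. A reader might also infer that the trial's results are at risk. They are not: fatal events keep their 7-day limit through the death criterion, and the CTX endpoint, the sample size and the efficacy analyses do not use this definition.

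**What to change.** Reword the note so that an adverse event counts as life-threatening when the patient's life was actually at risk while it was occurring, and does not count when it could only hypothetically have become fatal by progressing. No change to the criteria list or to the Section 8.5 limits is needed.

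Section 12.1 requires a written amendment signed by the sponsor and the investigator, and Section 13.1 requires Ethics Committee approval of all protocol amendments. A short note to sites should go with it, so that investigators and the sponsor's safety staff use the corrected definition. The cost is one sentence plus the amendment procedure. Design, treatment, sample size and endpoints stay as they are.

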### **Adverse event (AE) / adverse reaction (AR) severity**

The severity of serious and non-serious AE or AR should be evaluated according to the following criteria.

- Mild: no intervention or routine actions are required; for laboratory parameters, abnormality is considered mild.
- Moderate: no intervention or routine actions are required; for laboratory parameters, abnormality is considered moderate.

- Severe: intervention or routine actions are required; for laboratory parameters, abnormality is considered severe.

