**5.2 Fast-acting agents to relieve hypertensive episodes**

During the washout period and the rest of the study, use of short-acting agents to relieve hypertensive episodes, such as captopril and nifedipine, is allowed. However, patients must be instructed to refrain from these medications for 24 hours prior to the study visit in order to obtain accurate blood pressure data. At the visits, the investigator will ask if a patient took any short-acting drugs to relief hypertensive episodes; data and time of the last dose will be documented in the CRF.

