### **7.2 Methods and timing**

Methods and timing of the parameters identification are as follows:

**Physical examination.** During the patient screening and enrollment and at the final visit, the investigator will document the patient's complaints and abnormalities, detected on

physical examination. All clinically significant abnormalities should be reported as adverse events.

**Blood pressure and heart rate.** All patients will have their blood pressure and heart rate measured at every visit. If blood pressure and heart rate are abnormal, the investigator will evaluate the clinical significance of the abnormality and decide on whether to document it as an adverse event.

**Laboratory tests parameters:** creatinine (including creatinine clearance calculation according to Cockcroft-Gault equation), potassium, sodium, ALT, AST. Fasting blood samples will be obtained at screening and at the final visit. Results of the tests will be entered into the CRF. If the sample is lost, the investigator may order resampling if medically indicated (e.g., if invalid test results are suspected).

All clinically significant adverse deviations from the baseline (screening) will be reported as adverse events.

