#### **10.4 Safety analysis**

All safety data will be analyzed in the safety analysis population. Safety analysis includes identification of all adverse events, including serious adverse events at every visit following the screening.

Analysis of adverse events including serious adverse events will be conducted to determine the total number of AEs, the total number of patients with adverse events, the number of treatment-related adverse events, the number of AEs associated with product discontinuation and the number of voluntary withdrawal of informed consent.

Rate and severity of all adverse events and drug-related adverse events (i.e., at least “possibly” associated with the studied product) will be summarized by organ systems. Data on the product withdrawal due to adverse events will be summarized in tables. The safety results will be presented using descriptive statistics.

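### Mild and moderate adverse events share one criterion and the laboratory grades are circular, so the mild/moderate split in the planned severity summaries has no defined meaning

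*Combined protocol and SAP*

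**What the plan says.** The severity subsection under Section 8.2 sets one scale for every event: "The severity of serious and non-serious AE or AR should be evaluated according to the following criteria". There are three grades.

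- The entry at the bottom of the scale is "Mild: no intervention or routine actions are required; for laboratory parameters, abnormality is considered mild".
- One step up, the clinical wording does not change and only the label does: "Moderate: no intervention or routine actions are required; for laboratory parameters, abnormality is considered moderate".
- At the top of the scale the clinical wording is reversed: "Severe: intervention or routine actions are required; for laboratory parameters, abnormality is considered severe".

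Section 10.4, and the synopsis in the same words, commit to tabulating the result by organ system: "Rate and severity of all adverse events and drug-related adverse events". Section 10.4 adds that "The safety results will be presented using descriptive statistics".

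Section 7.2 determines what reaches the scale. Clinically significant adverse laboratory deviations from screening are to be reported as adverse events. For an abnormal blood pressure or heart rate the investigator is to "decide on whether to document it as an adverse event".

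**The concern.** A severity scale has to tell the investigator which grade to tick. Here two of the three grades have the same clinical text, so nothing in the protocol separates them. The laboratory clauses look like a second criterion, but each defines a grade by its own name.

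The severe grade raises a second problem. It depends on whether something needs to be done, which is different from how intense the event is. An intense event that needs no action cannot be graded severe. On the plain reading, a slight event that needs a routine action must be.

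At stake are the severity summaries promised in the synopsis and Section 10.4. Their mild and moderate rows would reflect each investigator's private convention. The trial is open-label (Section 3.1), so that convention is applied by someone who knows the treatment, and a monitor would have no written rule against which to query a grade.

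**Working it through.** No arithmetic applies, because the plan gives no figure on this point. The check sets the definitions side by side, tries both ways of reading them, and then traces where severity is used.

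**Step 1. Compare the grades.**

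| Grade | Clinical criterion | Laboratory criterion |
|---|---|---|
| Mild | Action not required | The name of the grade |
| Moderate | Identical to mild | The name of the grade |
| Severe | Negation of the above | The name of the grade |

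The clinical criterion has two outcomes for three grades. The laboratory criterion has no content for any grade.

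**Step 2. Try both readings.** The phrase used for mild and moderate can be parsed in two ways. Reading A: neither an intervention nor a routine action is needed. Reading B: no intervention is needed, or at most routine actions are.

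| What the event requires | Grades that fit, reading A | Grades that fit, reading B |
|---|---|---|
| Nothing | Mild or moderate | Mild or moderate |
| A routine action only | Severe | Mild, moderate or severe |
| An intervention | Severe | Severe |

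Under A, severe can be told apart from the other two, but mild and moderate cannot be told apart from each other. Under B that failure remains, and an event needing only a routine action fits all three grades. Neither reading produces a mild/moderate boundary.

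**Step 3. Apply it to a case from the protocol.** Section 5.2 says that "use of short-acting agents to relieve hypertensive episodes, such as captopril and nifedipine, is allowed" during washout and for the rest of the study. Suppose an abnormal blood pressure is recorded as an adverse event and such an agent is judged to be required. Under A the event is severe whatever its intensity. Under B the grade turns on whether the agent counts as an intervention or as a routine action, which the protocol does not say. If it counts as routine, all three grades fit.

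**Step 4. Look for another scale.** The rest of Section 8 covers causality, seriousness, expectedness, and monitoring and reporting. None of it defines intensity. No named grading system, effect-on-activity criterion or laboratory cut-off for severity appears in Section 7, Section 10 or the appendices.

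**Step 5. Trace what depends on the scale.**

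| Output or rule | Uses the severity grade? |
|---|---|
| Severity summaries (synopsis, Section 10.4) | Yes |
| Counts of events, patients affected, related events, and events tied to stopping the product (Section 10.4) | No |
| Seriousness criteria (Section 8.2) | No; they have their own list |
| Expectedness, SUSAR definition and reporting (Sections 8.2 to 8.5) | No; they rest on nature, seriousness, outcome and causality |
| Withdrawal because of an adverse event (Section 4.5) | No; this is the investigator's judgement |
| Primary endpoint, C-telopeptide (Section 3.10) | No |

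The damage stops at the first row.

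**The case against.** The strongest defence is that little depends on this. Safety is descriptive, severity is not an endpoint, and events that matter most for patient protection are caught by the seriousness criteria, which include lasting disability. This stands and limits the reach of the point. It does not give the planned tables a meaning.

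A second defence is that the text is a drafting or translation slip that sites would see through. That may explain the wording, but the documents do not tell a site what was intended, and sites that each repair the scale in their own way would not repair it alike.

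Three stronger conclusions are tempting, and the documents support none of them.

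- **That the severe category will be inflated.** The definition turns on whether action is required, not on whether the patient received any. A tablet taken by choice for a headache is not necessarily a required intervention. Equally, an event that needed intervention and got none is still severe. Under reading B, routine actions do not force the severe grade at all. The documents give no adverse event rates, so neither direction nor amount can be derived.
- **That a between-arm comparison by severity is lost.** Section 10.4 and the synopsis plan descriptive summaries and specify no such comparison. Grading that differs by arm is possible in an open-label trial, but it is not shown.
- **That no grades can be separated.** This is strictly true only for mild against moderate. On the plain reading, severe remains distinguishable, as a marker of action needed.

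Finally, the CRF adverse event form is not in the documents, so it cannot be said whether action taken is already recorded separately.

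**Conclusion.** The point holds in a limited form. It is an error in a stated rule, not a missing detail: a site that follows the text exactly has no basis for choosing between mild and moderate, or for grading any laboratory abnormality. This is so under both readings of the phrase. The severe grade measures need for action and not intensity, and under the second reading all three grades overlap for events that need only routine actions.

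The consequence is confined to the descriptive severity summaries. No numerical size can be given. The conclusion assumes that sites apply the protocol text as written and that no other instruction, such as one on the CRF, supplies a scale. The change is worth making because it is cheap, and because intensity never recorded against a usable definition may not be recoverable later.

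**What to change.** Before adverse events are graded:

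1. Replace the severity paragraph under Section 8.2 with three mutually exclusive definitions of intensity. Effect on usual activities (none, some limitation, prevented) is one workable basis. Any set that does not overlap would do.
2. Grade laboratory abnormalities by a named scale or by cut-offs for each analyte, covering high and low values. A single rule based on multiples of the normal limits would not serve, because the safety tests in Section 7.2 include potassium and sodium, and low values also need a grade.
3. Record action taken as an item separate from severity, if the CRF does not already do so.

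The cost is a short written amendment under Section 12.1, the ethics committee approval that Section 13.1 requires for amendments, and matching CRF instructions. If cut-offs are written instead of citing a named scale, each analyte needs its own. No visit, test or treatment rule changes. If events have already been graded on the present text, the report should say so and should not interpret the mild/moderate split.
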